To explore the proposed mechanism of change we will conduct a prognostic linear regression analysis to model the relationship between pre-randomisation factors; age, gender, ethnicity, IMD, SRDS, SDQ, BFRS, GHQ and observed outcomes at 6- and 12- months respectively on the primary outcome at either 6- or 12-months. Interaction terms with allocation arm will be included in the analysis, and a significance level of 0.1 will be used to determine which factors are to be included in the regression model. This analysis will be augmented by an additional

analysis including participants in the RBT arm only using the same pre-randomisation factors but also including process measures of compliance, therapeutic alliance, and interventionist attitude to trauma informed practice.

Interim analyses and stopping rules

No interim analyses are planned. The trial will only be stopped if evidence emerges of a serious adverse event associated with participation in the trial. As the intervention has already been implemented in practice with youth offending populations there is no evidence at the outset that a serious adverse event is likely to occur.

Longitudinal follow-up analyses

Assessments are conducted at baseline, prior to randomisation and then again at months 6 and 12, with 6-months being considered the primary endpoint. Table 2 provides an overview of what measures are being conducted at each time-point.

Outcome	No of items	Baseline	Six months	Twelve months
Primary				
Self-reported delinquency (SRDS) ¹	36	✓	✓	✓
Secondary				
Strength and Difficulties (SDQ) ¹	25	✓	✓	✓
Wellbeing (SWEBWMS)	7	✓	✓	✓
Psychological Distress (GHQ12)	12	✓	✓	✓
Family environment (BFRQ)	16	✓	✓	✓
Receipt Inventory (CSRI)	8	✓	✓	✓
Staff attitudes to trauma informed care (ARTIC)	35	✓	✓	✓
Staff wellbeing (SWEBWMS)	7	✓	✓	✓
Staff turnover & absence	2	✓	✓	✓
Exploratory				
Adverse childhood experiences (ACE-Q)	10	✓		
Process				
Therapeutic relationship	12		✓	
Proportion of sessions planned & delivered	1		✓	✓

Imbalance at baseline

Rather than just assume the randomisation has worked, we will assess observed balance by comparing the means and distributions of the groups created by randomisation for both participants and staff. If they are systematically different across those variables we observe – e.g. always larger / smaller in one group - then that would suggest the randomisation has not been successfully implemented. Baseline equivalence following randomisation will be

assessed by first looking at allocation by the three stratifying variables, service, sex and age group for participants and service and specialism for staff.

Baseline characteristics will be summarised by allocated group. Summary measures for the baseline characteristics of each group will be presented as mean and standard deviation for continuous (approximate) normally distributed variables, medians and interquartile ranges for non-normally distributed variables, and frequencies and percentages for categorical variables. Following CONSORT when comparing intervention and control groups we will not employ statistical testing.

If there is a large imbalance between groups on a specific variable, then that variable will be included in the analysis model. If there are systematic differences across multiple variables that are indicative of failed randomisation then it would be necessary to explore alternative analysis methods to estimate intervention effects, such as instrumental variable models, using allocation as the IV.

Missing data

The proportion of missing data and patterns of missingness will be examined for the primary outcome only, quantity of offences at 6-month post-randomisation. Levels of missing data will be reported along with any systematic occurrences of missing data observed in the dataset.

In trials some participants are inevitably lost to follow-up. Sample size estimation assumed 10% of patients would not provide an evaluable 6-month follow-up assessment. We will explore the mechanism of missing data to establish whether the data can be considered missing completely at random or missing at random. For each arm we will present baseline data for those followed-up at 6 months and those lost to follow-up and logistic regression analysis to explore for any systematic differences between the allocated group. If no predictor variables emerge from the regression model then the missing data can be classed as missing at random.

To avoid loss of efficiency missing outcome values will be imputed using multiple imputation, if the proportion of missing data is greater than 5% and less than 40%. Where there is less than 5% missing data, the proportion of missing data is considered negligible and missing observations will be excluded. Multiple imputation methods perform less well when the amount of missing data is substantial, if more than 40% of the primary outcome data are missing for the primary analysis the assumptions are less plausible. The interpretative limitations of the trial data will be discussed in the results section, where this is the case.

An initial variable reduction analysis will explore the relationship between all potentially prognostic baseline covariates and whether a follow-up data point is missing. Only variables where there is an association, p -value > 0.10 , will be included in the imputation model. The

association between the number of imputations will be dependent on the amount of missing data. As a minimum the number of imputations will be derived to ensure at least 96% statistical efficiency (*RE*) according to the formula below, where λ is the fraction of missing values and M is the number of repetitions (eq. 4).

$$RE = \left(1 + \frac{\lambda}{M}\right)^{-1}$$

The statistical model and assumptions made in the analysis of the primary outcome will also be implemented in the multiple imputation procedures. If it is suspected data is missing not at random or the pattern of missing data is associated with trial allocation, sensitivity analysis will be performed using a pattern mixture approach with mixed modelling and multiple imputation to compare the sensitivity of conclusions to varying assumptions about the missing value mechanism.

Intra-cluster correlations (ICCs)

The trial is individually randomised with stratification at the level of service, no ICC's will be calculated.

Compliance

To explore the role of compliance on outcomes we will conduct a Complier Average Causal Effects analysis (CACE). The definition of compliance with allocation for this trial is as follows (see Table 1 below): (i) those who receive trauma screening (TS) and 80% of RBT interventions offered will be considered 'compliers' in the intervention group (cell A); (ii) those in the control group who did not receive any RBT intervention (cell D). In the intervention group, those attending no trauma screening and/ or less than 80% of interventions offered will be considered 'non-compliers', (cell B). All non-compliers in the intervention group are regarded as being 'contaminated' because they received the control condition (no RBT interventions). For the control group, there is no option for control participants to access the intervention, so there cannot be non-compliance hence this is n/a (cell C).

To further explore the role of compliance on outcomes we will create several thresholds for intervention compliance;

1. TS versus no TS.
2. TS and/ or < 20% of RBT interventions versus TS and >= 20% RBT.
3. TS and/ or < 40% of RBT interventions versus TS and >= 40% RBT.
4. TS and/ or < 60% of RBT interventions versus TS and >= 60% RBT.
5. TS and/ or < 80% of RBT interventions versus TS and >= 80% RBT.

CACE analysis will be undertaken for each threshold and presented as a sensitivity analysis to allow a comparison of outcomes, (RBT group vs BAU) at different thresholds of compliance.

Table 1: Compliance/non-compliance according to group allocation versus intervention received.

	Actually received...	
Allocated to... ↓	Intervention	Control
Intervention	
A. Intervention complier
 
Meeting the stated threshold
	
B. Intervention non-complier
 
Not meeting the stated threshold

Control	
C. Control non-complier
 
n/a
	
D. Control complier
 
Control group participant

We will assess intervention effects in the presence of non-compliance, with compliance measured at the individual level and including all those allocated as part of the trial. Our approach for assessing intervention effects under non-compliance will be via the instrumental variable framework (IV). The benefit of using an IV approach is that randomisation is maintained in the analysis, which is crucial for estimating unbiased intervention effects. In summary, with a binary measure of compliance CACE weights the analysis by treatment allocated (ITT) intervention effect by the proportion of compliers (eq. 5):

$$CACE = ITT / \textit{proportion compliant}$$

If the proportion compliant is 1.0 (i.e. perfect compliance) then the CACE estimate is the same as the ITT estimate, but otherwise the impact of this approach is to increase the magnitude of the intervention effect.

CACE uses a two-stage least squares (2SLS). The first stage model uses intervention received (T) as the outcome, with random allocation (Z) as the independent variable (eq. 6):

$$T = \alpha + Z$$

Based on the stage 1 model, we then calculate predicted values of intervention received (\hat{T}) for use in stage 2. The second stage model predicts the substantive outcome (Y e.g. quantity of offences) using the predicted values of intervention received (\hat{T}) based on the stage 1 model (Eq.7):

$$Y = \alpha + \hat{T} + \varepsilon$$

An additional sensitivity analysis will employ a per protocol approach (PP), containing all data for participants who complete the trial as planned – in intervention and control groups - without any major protocol violations or exclusions. PP analysis essentially drop those individuals who have not strictly complied with their allocation – both those who only partially complied with their allocated intervention and those who did not receive their allocated intervention. This means that PP represents a likely ‘best case scenario’ for intervention effect estimation. The PP dataset will be analysed in a similar manner to the ITT dataset.

Presentation of outcomes

As the sample is large, effect size differences will be calculated using Cohen’s d, specified in the following equation (eq. 8):

$$\delta = (Y_i - Y_o) / S$$

Where Y_i and Y_c are the regression adjusted means, derived from eq. 1, for the intervention and control groups respectively and S is the pooled standard deviation.

Effect sizes will be reported with 95% confidence intervals and p-values to reflect statistical uncertainty.

youthendowmentfund.org.uk

[contact]

[@YouthEndowFund](https://twitter.com/YouthEndowFund)

The Youth Endowment Fund Charitable Trust

Registered Charity Number: 1185413

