The efficacy trial design is a mixed method, two level, individually randomised controlled trial of a trauma informed intervention, Trauma Recovery Model Relationship Building Together (RBT), versus business as usual (BAU) for adolescents and young adults served by Bridgend Youth Services (youth justice, edge of care, youth development and early help). There are two levels to the study randomisation. Level one involves selecting staff to be trained in RBT. This allocation is done for all staff, after baseline staff data collection, and is conducted by an on-line independent secure randomisation service, Sealed Envelope Ltd. Consent will be sought from all eligible staff prior to randomisation. As allocations are done at the same time and because we want to maximise balance across the groups on key parameters, we will employ minimisation for the allocation of staff. Our aim will be to maximise balance in terms of service (youth justice, edge of care, children's services, youth development, and early help) and speciality (specialised staff versus generic staff). Provision has been made to conduct a second wave of staff randomisation and TRM training if there is a high turnover of staff throughout the trial – a high turnover is one that exceeds 30%.

Level two allocation involves the randomisation of young people to RBT or BAU. This will be conducted by research staff, using a secure, on-line randomisation service (Sealed Envelope Ltd). after informed consent has been taken and the baseline assessment completed and before any trauma screening has been conducted. The allocation will involve an equal probability of receiving RBT or BAU and will employ random permuted blocks of variable size (4, 6 or 8) with a random block seeded throughout. Randomisation will be stratified by service (youth justice, edge of care, children's services, youth development and early help), sex (male, female), and age group (<15 years, 15 years or more). Stratification variables have been chosen to ensure allocation is balanced across services, sex, and age as some workers specialise in working with older or younger males and females.

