We have used an effect size difference of 0.25 as an important difference; this equates to a difference in volume of offences of circa 12% over a 6-month period, similar effects as found in other psychologically focussed interventions to reduce recidivism in adolescent populations (Hodgkinson et al., 2021). To detect this difference or greater, using a two-sided test, alpha of 0.05 and power at 80% requires 506 young people to be followed-up at our primary endpoint, 6-months post-randomisation, 253 in each group. There is no reliable literature on pre- and post-test correlations for the SRDS, so we have erred on the side of caution and not accounted for this in the sample size calculation as an incorrect assumption increases the risk of an under-powered trial. If we take a potential loss to follow-up of 10%, similar to attrition found in our other studies of young people (Coulton S et al., 2023) this inflates the required baseline sample to 562. We have 73 potential interventionists, 35 randomised to control and 36 randomised to be trained in the intervention delivery. Each interventionist can manage a harmonic mean of 10 young people through the course of the study. To achieve our target, we would need to have at least 56 of these interventionists participating throughout the trial, 28 in each arm, thus allowing for a potential loss of interventionists of 17, 23% of those available.

Assuming only 80% of young people approached consent to take part as found in similar studies (Coulton S et al., 2023) means we would need to approach 702 young people, over the recruitment period. Allowing for a slower start of 20/ per month recruited over the first three months, means 36 will need to be recruited in each month between January 2024 and February 2025, allowing for a six-month follow-up for the interim report submitted in September 2025.

Analysis

All analysis is conducted using STATA 16 SE. Analysis will be conducted and presented in accordance with the CONSORT guidelines. The validity of randomisation will be explored by presenting baseline measures of central tendency and estimates of precision for continuous variables, and proportions for categorical variables broken down by allocated arm and stratification factors for both staff and participant samples.

Primary outcome analysis

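### The SAP triggers a second staff training wave only above 30% turnover, although its own staffing figures tolerate a loss of only about 21% to 23%

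*SAP*

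**What the plan says.** **Staffing, SAP.** The Introduction provides for a second wave of staff randomisation and training under high turnover, and "a high turnover is one that exceeds 30" per cent. It also says that new staff can take part only if a second wave is planned. The Sample size calculations overview gives the pool: "We have 73 potential interventionists, 35 randomised to control and 36 randomised to be trained in the intervention delivery". Each interventionist is taken to manage 10 young people (a harmonic mean), and at least 56 are needed throughout, 28 in each arm, "thus allowing for a potential loss of interventionists of 17, 23% of those available". The SAP's summary table still lists 80 staff.

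**Staffing, protocol.** Sample size calculations starts from 80 interventionists, 40 per arm, with the same need for 56 and a tolerable loss of 24 (30%). The Randomisation section uses the same 30% trigger.

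**Recruitment, both documents.** After a slower start of 20 a month over the first three months, the target "means 36 will need to be recruited in each month between January 2024 and February 2025". The aim is 506 followed up, and with 10% attrition "this inflates the required baseline sample to 562". Neither text says whether the three slow months come before January 2024 or are the first three months of that window.

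**The concern.** The trigger is the plan's only stated route for replacing lost interventionists. In the protocol it and the tolerable loss are the same number, so the second wave is called once the floor is breached. The SAP reduced the pool and recalculated the tolerable loss, but left the trigger at 30%. The safeguard now acts after the trial has fallen below the staffing that the SAP says it needs. The trigger also refers to staff overall, whereas the requirement is 28 in each arm.

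The stake is delivery capacity. The sample size has almost no slack (80.3% power at 506 followed up), so a capacity shortfall that lowers recruitment takes unadjusted power below the 80% target.

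A secondary question concerns the monthly target of 36, which gives different totals depending on where the slow months fall.

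**Working it through.** **1. The plan's sample size.** Inputs from the SAP's sample size section: effect size 0.25, two-sided alpha 0.05, power 80%.
- n per arm = 2 × (1.96 + 0.8416)² / 0.25² = 251.2, so 252. The t-test version gives 252.1, rounded up to 253, or 506 in total. Reproduced.
- 506 / 0.90 = 562.2. Reproduced as 562.
- 562 / 10 = 56.2. The plan uses 56 (56 × 10 = 560, a trivial difference).

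**2. Tolerable loss = (pool − 56) / pool.**

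| Pool | Source | Tolerable loss |
|---|---|---|
| 80 | Protocol | 24 (30.0%) |
| 73 | SAP, stated total | 17 (23.3%) |
| 71 | SAP, 35 + 36 | 15 (21.1%) |

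By arm on the SAP's split, with a floor of 28: control (35 − 28)/35 = 20.0%; RBT (36 − 28)/36 = 22.2%.

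**3. The uncovered band.** The floor is breached at one loss more than the tolerable number. The trigger fires at the first whole number above 30%.
- Pool 80: the floor is breached at 25 lost and the trigger fires at 25 (31.3%). No gap.
- Pool 73: breached at 18 lost (24.7%), fires at 22 (30.1%). Losses of 18 to 21 are uncovered.
- Pool 71: breached at 16 lost (22.5%), fires at 22 (31.0%). Losses of 16 to 21 are uncovered.
- One arm only: losing 8 of 35 control staff leaves 27, below 28, yet is 8/71 = 11.3% overall.

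**4. Size at the edge of the band.** Power is approximated by Φ(0.25 × √(N/4) − 1.96), unadjusted, with N the number followed up.
- 21 of 71 lost (29.6%) does not fire the trigger. It leaves 50 staff, 50 × 10 = 500 places, and 500 × 0.9 = 450 followed up. Power is Φ(2.652 − 1.96) = 75.5%.
- 21 of 73 lost (28.8%) leaves 52, also below 56.
- No losses: 710 to 730 places, against 562 needed.

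**5. Recruitment.** January 2024 to February 2025 is 14 months.
- Slow months before the window: (562 − 60)/14 = 35.9, so 36. The total is 60 + 14 × 36 = 564. This reproduces the plan's figure and covers 562.
- Slow months inside the window: 60 + 11 × 36 = 456, about 410 followed up, unadjusted power about 72%. Reaching 562 would need 502/11 = 45.6, so about 46 a month. At 36 a month it would take 3 + 502/36, about 17 months. From January 2024 that ends around May 2025, with the last six-month follow-up around November 2025.
- Dates: the original protocol is dated 23/01/24 (Protocol version history), and its Ethics and registration section describes recruitment, ethical approval and registration as still to come.

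**The case against.** **Staffing.** The undepleted pool is ample, so it would be wrong to infer that the staffing figures cannot support 562. That stands; the fault is confined to the band between tolerance and trigger. The 500 places are also an unfavourable case. Turnover accrues over the whole trial, and staff who leave late have already carried cases. The caseload of 10 is a harmonic mean, which cannot exceed the arithmetic mean that governs total capacity. The protocol also describes youth justice staff already trained in RBT and outside the staff randomisation, who may add RBT capacity, though not control capacity. All of this limits the size of the consequence. None of it reconciles a 30% trigger with a 23% tolerance.

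**Definition and count.** Turnover is not defined and might not mean loss of interventionists, although the protocol's matching 30% figures suggest that it does. Nor can 71 be taken as the true count: the SAP's 17 and 23% follow from 73, so an arm size may be the misprint.

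**Power.** The 75% ignores baseline adjustment, which the SAP plans but leaves out of the sample size from caution. The documents give no correlation. Assuming 0.3 to 0.5, power at 450 would be about 79% to 86% before any clustering. A loss of power below 80% is therefore possible but not established.

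**Recruitment.** A reader might conclude that 36 a month yields 456. The documents do not establish that: they ask for 36 in every month of the window, and with 60 earlier recruits that gives 564. A protocol version date is not a recruitment start date, and the Gantt chart to which the protocol refers is not in the documents reviewed. What stands is that three recruiting months before January 2024 are hard to square with the dates and the future tense.

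**Conclusion.** The staffing point holds as an internal contradiction. The SAP's trigger of more than 30% exceeds its own tolerable loss of 23% (17 of 73) or 21% (15 of 71), and 20% to 22% by arm on the stated split. Because new staff enter only with a second wave, losses of 18 to 21 of 73, or 16 to 21 of 71, leave fewer than 56 with no replacement called for. This rests on turnover meaning loss of participating interventionists. The figure of about 75% power is an illustration that also assumes early losses, 10 young people each and no baseline adjustment.

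The recruitment point is secondary and is an ambiguity, not a demonstrated shortfall: 564 if the slow months precede January 2024, 456 if they fall inside the window. The dates make the second reading likely but do not prove it. Nor does it follow that 506 followed up and 80% power are missed either way. Recruitment could run on to about May 2025 and still reach 562, in which case the loss would be to the September 2025 report.

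**What to change.** 1. Reconcile 80, 73 and 71 (35 + 36) across the SAP's summary table and sample size text, and restate the tolerable loss from the reconciled count.
2. Define turnover, for this rule, as loss of participating interventionists.
3. Set the second-wave trigger by arm, so that it fires before either arm falls below 28. It should be no higher than the restated tolerance (about 20% to 23% on the present figures).
4. State the date on which recruitment starts and the monthly target that follows from it: 36 if the slow months precede January 2024, about 46 if they fall within January 2024 to February 2025. Alternatively, state the number expected in the September 2025 report.

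The cost is mainly wording. The second wave is already provisioned, but it may be called earlier and more readily than under the 30% rule. If the slow months fall inside the window, a harder monthly target or a smaller September 2025 dataset has to be acknowledged.
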